#### Risks of Unsecured Communication

Participants will be contacted via phone and secure text messaging. Phone communication will not be secured putting the participants at risk of having PII inadvertently disclosed. Secure text messaging is subject to hacking.

### 13. Benefits

Participants in the study may develop a greater personal understanding of how their lifestyle habits (e.g. physical activity, diet) affect their glucose levels (e.g. average glucose, PPG, GV, and NG). What they learn will help them understand better how to self-manage their glucose and be healthier. Information gained from this program will be used to further refine the program so that it can benefit more people.

### 14. Compensation

During the study, participants will use a free Fitbit Charge 2 activity tracker and a Dexcom CGM system for 10 weeks. Study participants will also have access to their personal CGM data (up to 24 hours) via the Dexcom CGM system app while using the CGM system and in a summary report after they have finished

using the system. During the 10 weeks of CGM use, participants will receive free over-the-phone and secure text messaging communication with coaches related to CGM and diabetes self-management.

To compensate participants for the time it will take to get set-up and use their devices (e.g. receive a home visit/attend a class/attend an in-clinic meeting, or seek other assistance; study and understand program materials; maintain device function via calibrations and charging, return study devices, etc.), patients will be compensated up to a total of \$250 according to the following schedule:

Study task	Compensation
Wearing a Dexcom® CGM sensor for the first 10 days and wearing Fitbit Charge 2™ for 7 out of those 10 days	\$190
Wearing a CGM sensor for each additional 10 days and wearing Fitbit Charge 2 for 7 out of those 10 days	\$10 (total not to exceed \$60)

Patients need not wear their 10-day sensors continuously, nor will they need to wear the same sensor for 10 days in order to qualify. Compensation will be provided in the form of a gift card after the participant has completed the program, or upon withdrawl from the study, whichever comes first.

Participants may be invited to continue to wear and upload data from their activity trackers (defined as syncing at least every three weeks through August 31, 2018). Patients will return the smartphone and activity tracker to the Sponsor at the end of the study.

Patients who received a glucometer (\$40) may keep it.

Study participants will also continue to have access to their personal physical activity dashboard after the study ends.

## 15. Quality Control and Quality Assurance

All study staff interacting with patients will receive training in the fundamentals of the ethical treatment and safety of human subjects. The Principle Investigator will be responsible for assuring that program staff receive this training and that the entire research team adheres to the protocol. The Principle Investigator will also ensure that the principles of Good Clinical Practice are being followed.

In addition, the research team participating in this study represent individuals whose qualifications and experience have equipped them to collect and analyze confidential patient data. The study's medical advisors (Co-Investigators) will meet with the Principle Investigator to review progress and offer any direction that may be needed with regard to patient safety. The HITRUST-certified environment in which data will be stored will provide a high level of protection for all data collected (see below).

## 16. Ethics

The proposed program will involve patients with a medical condition. The program recruitment strategies assure that prospective patients have access to a staff member with whom they can discuss and ask questions about the program before signing an informed consent form and then while participating in the program. Patients who receive study materials in the mail will have a minimum of two days to review study materials and ask questions of research staff before signing and dating the informed consent form. Patients who meet with study staff (e.g. at a home visit, educational class, or in-

clinic meeting) will be given ample time to read the consent form and as much time as needed to talk with a program representative about the study. There is no limit to the number of times patients may speak with program staff before making a decision about whether to participate.

As some participants may not want their condition to be known to others, they will have the option and resources to start using the CGM system without having to attend a class. The program will serve as an adjunct to normal medical care.

Patients will have the freedom to use the CGM system and activity tracker at times of their choosing. They will be participating at-will, may withdraw from the study any time, and will face no adverse consequences from the program or their providers if they withdraw from the study or choose not to participate at all.

We want this study to be minimal risk. As such not all patients with T2D will be eligible. The inclusion/exclusion criteria preclude certain patient populations with T2D that would benefit from participating in the study. However, resource constraints and the management of risk do not allow for all patients with T2D to participate at this time.

## 17. Data Handling and Record Keeping

Data will be collected by these entities:

- Savvysherpa will collect medical record data and claims cost data from participants' medical records.
- Dexcom will collect interstitial glucose data and data related to device use (such as calibration timestamps) from participants in the CGM program.
- Savvysherpa will collect program data from the participants directly and from the program. Program data will include survey responses, call recordings, coach-patient secure texts, and/or in-person group participation at educational classes.
- Fitbit will collect data from activity trackers.

Dexcom, Fitbit, and provider data will be shared with Savvysherpa. Savvysherpa will have access to versions of the data that include personally identifiable information (PII) and protected health information (PHI) from all of these entities.

PHI will be extracted from the following sources and brought into Savvysherpa's study infrastructure—a HITRUST-certified secure server environment.

- Savvysherpa will work with providers to assure secure data transfer of medical record and claims cost data.
- Claim records and medical records stored in a physically secured room will be accessed by an authorized party, extracted from the room using documented procedures, and loaded into the study infrastructure.
- Dexcom CGM patient readings will be sent from Dexcom secure servers over a secure, encrypted connection to the secure, encrypted study cloud infrastructure.
- Data from the activity trackers will be synced via Bluetooth to the client's application. From the application, the data will be sent via https to the client's secure servers. From the client's secure servers, the data will be sent to Savvysherpa via https.

- Authorized program advisors will communicate with patients via phone call, and also by secure text messaging to smartphones issued to each patient. Messages will be delivered to an app utilizing patient's credentials over an encrypted connection to the messaging server. Data, notes, and recordings related to these transactions will be stored within the study infrastructure.

Within the study infrastructure, communication between servers and data stored on servers will be encrypted and accessed via login by authorized personnel for the purpose of assisting and advising patients in the program, and for conducting related analysis and program optimization.

The combined dataset will be de-identified by removing personal identifiers from each system and replacing them with a unique study identifier. A list connecting personal identifiers and the unique identifier will be maintained and stored by Savvyshera in a separate password-protected database. Any links between personal identifiers from the source systems and study identifier will be deleted 10 years after the completion of the study. Recordings of coaching sessions and group participation activity will also be deleted 10 years after the completion of the study.

Over the course of the program Savvyshera will have the PII necessary to allow for patient contact as outlined in the protocol. This will be described in the informed consent document.

## 18. Financing and Insurance

The Sponsor of the study is Savvyshera, Inc. Some or all funding for this program will be provided by Savvyshera and/or its affiliates.

## 19. Publication Policy

The investigators intend to publish on the proposed implementation activities or results.

## 21. Supplementary Materials (uploaded)

The Investigator's Brochure for Dexcom's investigational CGM system will be uploaded as part of our argument that this is a Non-Significant Risk device.

## 22. Appendix A

### Piloting the Dexcom CGM System with Medicare Type 2 Patients: Phase 1

September 2016

#### Executive Summary

As part of a health system's diabetes quality improvement initiative, we created an educational program for Medicare patients with type 2 diabetes incorporating the Dexcom G5 continuous glucose monitoring (CGM) system and activity trackers. In this initial two-week pilot program, we wanted to learn about patients' recruitment rates, compliance with device tasks, and general responses to the CGM system and program model.

#### Recruitment

- We called 60 patients to invite them to the program, reaching 39 (65%) of patients by phone.
- 16 (27%) accepted the phone invitation.
- 11 (18%) participated by attending the in-service and applying their first CGM sensor.

#### Compliance

- In week one, 10 out of 11 participants independently calibrated their first CGM sensor after the sensor's two-hour warm-up period.
- In week two, 8 out of 11 participants independently applied and calibrated their second CGM sensor after the sensor's two-hour warm-up period.

#### General responses

- Participants joined the program primarily because of their physicians' recommendations.
- Participants either 1) quickly understood the potential for using CGM to identify behaviors that impact their glucose, or 2) did not demonstrate an understanding of this relationship and would need more support to do so.
- Many participants struggled with the small-motor skills needed to apply the CGM sensor and transmitter and to press buttons on the receiver and activity tracker.
- Roughly half of participants were interested in using the CGM system again to manage their diabetes.

#### Conclusions

Based on these findings, we conclude that:

- A portion of this population will wear a CGM device and can, with training, remove and apply CGM sensors by themselves.
- With support for their individual needs, this population can benefit from using CGM to understand and manage diabetes.
- Participants need more time and coaching to use CGM devices confidently and to understand their data.
- Sharing patients' data with program staff would allow the program to design and provide relevant support for those patients.

#### Recommendations

To continue to develop this program, we recommend:

- Phase 2: Implement and observe other methods of delivering devices, educating patients, and obtaining patients' CGM data.
- Phase 3: Based on findings from phases 1 and 2, design and test this program on a larger scale with the goal of improving patients' A1c levels.

## 23. Appendix B

### Adverse Events Severity and Relatedness Questions

May 2017

When patients share a complaint, program coaches will identify the complaint in the Anticipated Complaints Guidebook. Based on the complaint type, coaches will then ask questions to determine:

1. Severity of the complaint (e.g., Mild, Moderate, or Severe), and
2. Relatedness of the complaint to the use of program devices (e.g., Not Related, Probably Not Related, Possibly Related, and Probably Related)

Coaches will document answers in the templates provided, including the Adverse Event document.

If the complaint falls in any of the severity categories highlighted in red, the coach will make a “warm transfer” to the study doctor and/or his staff so that the patient can be scheduled for an ancillary appointment.

If the complaint is an emergency, patients will be instructed to call 911.

If a patient has a complaint that is not listed in the Anticipated Complaints Guidebook, the coach can “warm transfer” the patient to the study clinic for guidance. The coach will document as much as possible in Adverse Event document. Follow up with the clinic will determine severity and relatedness.

Coaches will contact the PI when situations arise that are not covered in the Anticipated Complaints Guidebook.

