- Study coaches will listen for any reports of AE or SAE or UP in the course of their communications with participants, and will connect reporting patients with the study doctor's clinical research coordinator so events can be assessed and documented and patients can receive care, if needed.
- Any reports of AE or SAE or UP received by Dexcom's Technical Support representatives will be documented and reported to the Sponsor. Coaches will then promptly notify the study doctor's clinical research coordinator of these reports so that the coordinator can then follow up with the patient to assess event severity and relatedness, and schedule the patient for care, if needed.

The Sponsor-Investigator will receive CGM-related AE and SAE and UP information from Dexcom through secure data transfers. AE and SAE and UP information from the study doctor will also be stored and transferred securely. Any other records pertaining to AE and SAE from patient conversations with program staff will be recorded and documented using call-management software and the patient's Case Report Form.

The Sponsor-Investigator will ensure proper reporting of AE and SAE and UP to Chesapeake IRB, the CGM manufacturer, the FDA, and any other regulatory bodies according to regulations and standard operating procedures. (See Appendix C for a chart illustrating the reporting process, and Appendix B for AE assessment guidance for coaches.)

Patients will be provided with a summary printout of their recorded CGM data at the end of their participation with CGM. Patients can request a summary printout anytime during the trial. Patients can share their CGM data with their providers.

The Standard of Care guidelines associated with the program direct patients to seek medical care when needed. Guidance exists within the guidelines to seek medical advice when glucose values are extremely high over long periods of time, fluctuate rapidly from high levels to low levels and vice versa, or a

pattern of low glucose values is present. Coaches will remind patients of these guidelines but will not give medical advice. Coaches can send summary CGM data to patients upon patient request.

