Because the CGM data is an adjunct to patients' diabetes care, the investigator and research staff will NOT constantly monitor patients' realtime CGM data nor will research staff and coaches contact patients' medical providers on behalf of patients when low or high CGM values are observed. Patients will be responsible for using the blood glucose meter to manage their diabetes and to seek medical attention when needed.

Episodes of hyperglycemia or hypoglycemia that require patients to seek medical attention will be considered an AE or SAE depending upon the situation.

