#### **Skin Itchiness – Severity Category**

1. On a scale of 1 to 10, where 1 is very little, and 10 is severe, how would you rate your skin itchiness?
  - If 1-5, do not record as AE
  - If 6-7, Mild AE
  - If 8-9, Moderate AE
  - If 10, Severe AE**

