#### **Insertion Site Pain or Discomfort – Severity Category**

1. On a scale of 1 to 10, where 1 is very little, and 10 is severe, how much does your pain or discomfort affect your ability to do your daily activities?
  - If 1-2, do not record as AE
  - If 3-5, Mild AE
  - If 6-8, Moderate AE**
  - If 9-10, Severe AE**

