### **Insertion Site Bleeding – Severity Category**

1. Has the bleeding stopped?
  - If no, then: “Is the spot of blood greater than the size of a nickel?”
    - If no, then stop.
    - If yes, then **Severe AE**
  - If yes, then: “Is the spot of blood greater than the size of a nickel?”
    - If no, then stop.
    - If yes, then **Severe AE**

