### **Insertion Site Infection – Severity Category**

1. Do you notice signs of infection that include inflammation, drainage, pus discharge and pain?
  - a. If no, then stop
  - b. If yes, on a scale of 1 to 10, where 1 is very little and 10 is severe, how much inflammation, drainage, pus discharge and pain do you have?
    - If 1 – 8, **Moderate AE**
    - If 9 – 10, **Severe AE**

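### Five coach scripts set aside low-rated site reactions as non-AEs and none of the eight asks about medical care received, so a treated reaction may escape AE and seriousness assessment

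*Combined protocol and SAP*

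**What the plan says.** Section 9 (Assessment of Safety) gives coaches a part in detecting events: "Study coaches will listen for any reports of AE or SAE or UP". It names Appendix B as the coaches' guidance for assessing AEs and Appendix C as the chart of the reporting process.

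Appendix B has coaches grade "Severity of the complaint (e.g., Mild, Moderate, or Severe" and then relatedness. It adds: "Coaches will document answers in the templates provided, including the Adverse Event document".

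The Skin Itchiness script says "If 1-5, do not record as AE". The redness, swelling and bruising scripts use the same cut-off. The script for insertion site pain says "If 1-2, do not record as AE". Bleeding is graded by size: "Is the spot of blood greater than the size of a nickel". The infection script first asks about signs and, if there are any, "how much inflammation, drainage, pus discharge and pain do you have".

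For glucose episodes, Section 9 uses a different kind of criterion: "Episodes of hyperglycemia or hypoglycemia that require patients to seek medical attention will be considered an AE or SAE".

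**The concern.** A self-rating measures how bad the complaint feels when the question is asked. It does not measure whether the reaction needed treatment or admission. The severity questions are mostly in the present tense, and during CGM use the coach's scheduled contact is a weekly call (Section 6, CGM-based education and coaching). A participant treated between calls rates what is left after treatment, and that rating can fall in the range the script excludes.

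The device is investigational. Section 9 has AEs, SAEs and unanticipated problems reported to the IRB, the manufacturer and the FDA, and Section 10 says the study will inform a larger one. Reactions that needed care matter most for both purposes.

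**Working it through.** The plan gives no figure to reproduce here, so the check is a reading of the eight Appendix B severity scripts, set beside the capture routes in Sections 6 and 9.

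| Script | Graded on | Outcome with no AE grade | Asks about care received |
|---|---|---|---|
| Redness or rash | 1-10 rating | 1-5, unless the itch or pain questions give a grade | No |
| Itchiness | 1-10 rating | 1-5 | No |
| Site pain | 1-10 effect on daily activities | 1-2 | No |
| Swelling | 1-10 rating | 1-5 | No |
| Bruising | 1-10 rating | 1-5, unless the bruise is growing | No |
| Bleeding | Size of blood spot | Not larger than a nickel | No |
| Infection | Signs, then 1-10 rating | No signs at the time of asking | No |
| Broken wire | Wire visible, then 1-10 rating | Wire not visible | No |

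Counts:
- 7 of 8 scripts use a 1-10 rating; bleeding does not.
- 5 of 8 tell the coach not to record a low rating as an AE.
- The other 3 of 8 have a branch that stops without a grade. Since 5 + 3 = 8, every script has at least one path with no AE grade.
- 0 of 8 ask about a doctor's visit, emergency care or admission.

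The excluded range is 5 of 10 scores for redness, itch, swelling and bruising, and 2 of 10 for pain. In the redness script the gap is narrower than its first line suggests. To leave with no grade, a participant needs redness of 1-5, itch absent or 1-5, and pain absent or 1-2, because pain of 3-5 is already graded Mild.

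A hypothetical case shows the effect. A participant has site swelling, is treated at urgent care, and rates the swelling 3 at the next call. The script returns no AE and asks nothing more. A glucose episode that required the same care would be an AE or SAE under Section 9.

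On the broken wire, two passages conflict. Section 9 tells a participant with a broken sensor and no visible portion to seek medical care from the study doctor or staff. The Appendix B script, for the same finding, stops with no grade.

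Other capture routes:
- Section 6 (Integration with patient care): a potential study-related concern mentioned to a coach leads to contact with the study doctor. No rating threshold applies.
- Section 9: participants are told to call the study doctor's coordinator about device-related events.
- Section 9: coaches connect participants who report an event with that coordinator, for assessment and documentation.
- Section 9: reports made to the manufacturer's technical support reach the Sponsor, and the coordinator follows up.

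All four start from something the participant says. None has staff ask about care received.

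**The case against.** The strongest reply is that the scripts are only one route. A participant who says they were treated or admitted should reach the study doctor or coordinator whatever the rating, and the coordinator assesses severity and relatedness afresh. Coaches document the answers, calls are recorded, and Section 10 collects medical records and claims through 2027. Infection with signs present is at least a Moderate AE at every rating, and a visible broken wire is an AE at every rating; infection is a plausible reason for seeking care.

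All of this stands, and it rules out two stronger readings. A reader might infer that a low-rated, treated reaction leaves no trace. The documents do not support that: the instruction concerns classification as an AE, and the answers are still written down. A reader might also infer that all site complaints are affected alike. They are not, for the reasons just given and because of the redness and bruising overrides.

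The reply does not close the gap. The other routes depend on the participant volunteering the care. Section 9's own definitions for itch, redness, inflammation and shooting pain rest on intensity or persistence, not on care received. No section uses claims or medical records to detect AEs.

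It is also fair to say that receiving care does not make an event serious. That argues for a separate seriousness field, not for leaving the question out.

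**Conclusion.** The point holds as a gap in prompting and classification, and it should be fixed. For five complaint types, a reaction that was treated or led to admission but is rated low at the call may not be classified as an AE or assessed for seriousness, unless the participant mentions the care or another route catches it. The broken-wire contradiction is a separate matter and is plain in the text.

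The size can be stated only as counts of scripts: 5 of 8 exclude low ratings and 0 of 8 ask about care. A reader might try to turn the planned 500 participants into a number of missed events. The documents give no rate of care-seeking and no share of treated reactions rated low, so no such number can be derived.

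The conclusion assumes that the scripts are used as printed. The Anticipated Complaints Guidebook and the Appendix C chart are not in the supplied text, and the red highlighting that triggers transfer to the study doctor cannot be seen. Any of these might add a relevant question or step.

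**What to change.** Add one question to each of the eight scripts: whether, for this complaint, the participant saw a doctor, went to urgent care or an emergency room, or was admitted to hospital. Any yes should:

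1. override both the non-recording instruction and the stop branches;
2. be entered in the Adverse Event document;
3. go to the study doctor's coordinator, who records serious or not serious in a field separate from mild, moderate or severe.

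Reconcile the broken-wire script with Section 9; which of the two is right is for the investigators to decide. Check the Guidebook and the Appendix C chart first. If either already asks about care, refer to it from Appendix B.

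The cost is one question per script, one field on the form and slightly longer calls. A few more AEs will be recorded, some of them routine visits, which the seriousness field will separate out. The change concerns recording only and leaves clinical care as it is.
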